OUTCOME(S)	
Primary efficacy endpoint is the clinician-rated Hamilton anxiety score (SIGH-A). Key secondary endpoint(s): CGI total score, patient rated generic (BSI) and diagnosis-specific symptom scores (i.e. FFS, PAS, MI), impairment/disability days (CIDI Harvard Index, SDS), depression (dimensional: BDI, categorical: CIDI) quality of life (EQ-5D) and social functioning (SAS). As an objective and ecological valid measure for exposure trials we use a novel combined mobile mobility-EMS tool (see proposal ESPRIT). The range of measures is meant to demonstrate that IPI is associated with more pervasive changes in various domains. As proxy measure for extinction learning we use subjective measures of within-session and between-session exposure effects (anxiety ratings, expectancy ratings of central concerns). (Note: see further assessments in P3-P6.)
 
Assessment of safety: suicidality assessment and adverse behavioural effects.

STUDY TYPE	Randomised controlled clinical trial with two active conditions associated with mediator and moderator analyses (see projects P3-6)
STATISTICAL ANALYSES	
Efficacy: HAMA total score (standardized interview, SIGH-A)
 
Description of primary efficacy: Superiority of IPI against TAU will be tested with t-tests for independent samples using an alpha level of 0.5. Intent-to-treat (ITT), completer analyses will be conducted and mixed models (saturated for the joint effects of treatment group and time) fit to address dropout.
 
Safety: N/A
 
Secondary endpoints: ITT, completer analysis and mixed models as above but with two-sided tests in case of explorative analyses. Pearson correlations between dimensional comorbidity measures and outcomes will be calculated, Associations with categorical predictors will be analyzed with linear regressions.

SAMPLE SIZE	
To be assessed for eligibility n=1.400
 
To be allocated in a stratified way (by diagnosis) to trial (n = 720)
 
To be analysed (n = 620)

TRIAL DURATION	
First patient in: 6/1st year – last patient out (fup): 1/4th year
 
Recruitment and enrolment: start: 6/1st year
 
Duration of the entire trial: 36 months
 
Recruitment period: 6/1st year – 5/3rd year

CENTERS	7: Greifswald, Berlin, Münster, Marburg, Dresden, Bochum, Würzburg

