Extinction learning comprises several distinct phases: 1. The individual learns that a fear cue is no longer followed by the expected aversive consequences under the current circumstances or in the current context. 2. This learning experience is consolidated, and inhibitory associations are reinforced by repetitive exposure sessions. 3. In case of successful long-term extinction learning, extinction memory is recalled even if the previously feared cues occur in different contexts. Under critical circumstances recall of the extinction memory can be blocked and return of fear and even relapse can occur. Comparable learning and extinction processes are also important for contextual fear conditioning which occurs when aversive events appear unpredictable so that the context becomes the best, albeit imprecise, predictor of aversive events. Such contextual fear conditioning is an experimental model of sustained anxiety and explains avoidance and safety behavior at least in panic disorder patients.

We acknowledge that there are various constructs and paradigms to assess extinction-related mechanisms of change (e.g. enhanced discrimination learning, enhanced safety learning, reduced vulnerability to reinstatement, or context renewal). However, we refrain from providing here a complete critical review of evidence. Instead we present a review of evidence and highlight the following critical state of the art reviews (see also P3-P5).

Preclinical evidence: Although being far from consistent, animal and human studies on the timing of extinction trials suggest that massed extinction can result in enhanced fear inhibition, albeit possibly more susceptible to return of fear in the long-term. Early *animal research* suggested that massed extinction resulted in more rapid extinction learning. However, some studies found no effects, opposite effects, or have found that massed extinction even results in greater return of fear. In mice, the most effective method of enhancing extinction is found with initial massed trials followed by subsequent spaced trials. In *human subjects*, evidence on the inter-trial interval in extinction is scant, and many of the

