*To conclude, condensed exposure with short ITI results in faster extinction than spaced. This might however be at the expense of return of fear and clinically a higher chance of relapse. Therefore in the initial active treatment phase more trials with shorter ITI should be most promising for a rapid and more effective extinction learning. To stabilize this, subsequent spaced trials in different contexts is preferred.*

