### **2.2.8 Proposed sample size and power calculations**

Focusing on the HAM-A total score as the core primary outcome measure for determining the sample size, we expect - building on the meta-analytic results and pilot tests - that patients in IPI group will reduce the HAM-A-score (end of treatment) by 12 points. In the TAU group we expect a reduction by 10 points. Using a power of 80%, a test significance level of  $\alpha = 5\%$ , a standard deviation of 10 points and a one-sided t-test to detect differences between the IPI and TAU group, a total of 310 patients are needed per group. Based on previous such trials  drop-out rates during treatment including follow-up of 10%-15% are expected. Total n to be enrolled is 720 and to be analyzed 620.

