## 2.3 Statistical analyses

Statistics for the core primary outcome measure (HAM-A): In order to demonstrate that the IPI and TAU treatments differ, we use a one-tailed t-test with the following hypotheses:

$H_0: \mu_{\text{HAMADiff-IPI}} = \mu_{\text{HAMADiff-TAU}}$ ;  $H_A: \mu_{\text{HAMADiff-IPI}} > \mu_{\text{HAMADiff-TAU}}$ .

Here  $\mu_{\text{HAMADiff-IPI}}$  and  $\mu_{\text{HAMADiff-TAU}}$  are in each case the differences between the HAM-A baseline and the HAM-A value after the end of therapy in the treatment groups IPI and TAU.

Trial data will be analyzed both on an intent-to-treat (ITT) and per-protocol basis. To test whether groups have different outcomes for the major end points at (i) post and (ii) follow-up t-tests for independent samples will be used one-sided with an alpha level of 0.5. This will be also done for secondary and explorative analyses (in that case with two-sided tests). To quantify effect sizes for differences between groups at post-treatment and at follow up Cohen's d (with the pooled standard deviation at baseline in the denominator) will be used. To assess temporal changes in symptoms we will compare scores at initial assessment with those at t1 through t5. Individual outcome as a function of pretreatment characteristics will be modeled with multiple linear regression and associated analyses of variance.

Data will be analyzed with STATA and, if necessary, statistical weights will be used to adjust for different sampling probabilities in different study centers. LOCF-analyses (intent-to-treat) will be carried out as well as completer analyses and mixed models (saturated for the combined effects of time and group on outcome) to assess whether dropout changes the conclusions. Moderator analyses (predictors of treatment effects within IPI and TAU patients) will address type, respectively group of disorders as well comorbidity using dimensional and categorical measures. Pearson correlations between such comorbidity measures and outcome will be calculated. Associations with categorical predictors will be analyzed with linear regressions using dummy variables and quantified with mean differences in treatment outcome (and their 95% confidence intervals).

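### HAM-A at follow-up is tested one-sided for IPI superiority with no confidence interval for the arm difference, so a worse 6-month outcome under IPI has no formal inference

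*Combined protocol and SAP*

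**What the plan says.** Section 2.3 introduces the primary test with the words "In order to demonstrate that the IPI and TAU treatments differ, we use a one-tailed t-test". The alternative it then sets out has one direction: the HAM-A change from baseline to end of therapy is larger under IPI than under TAU. No separate hypothesis is written for follow-up. The same section then says that "at (i) post and (ii) follow-up t-tests for independent samples will be used one-sided", so week 34 takes over the direction set for end of therapy. The Summary's primary hypothesis is likewise superiority of IPI at both times.

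Section 2.2.8 sizes the trial with "a one-sided t-test to detect differences between the IPI and TAU group", at 5% and for the end of treatment only. Sections 2.3 and 0 print a different level: "with an alpha level of 0.5" and "using an alpha level of 0.5".

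For estimation, section 2.3 plans Cohen's d at post and at follow-up. It also plans mixed models saturated for time and group, to see whether dropout changes the conclusions. The only 95% confidence intervals it names belong to the analyses of categorical predictors of outcome.

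On the long-term effect of massed extinction, section 1.1 says of the preclinical evidence that it is "albeit possibly more susceptible to return of fear in the long-term". Its conclusion on condensed exposure is "This might however be at the expense of return of fear and clinically a higher chance of relapse". It then proposes later spaced trials in varied contexts as the remedy.

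**The concern.** A one-sided test fits best when a result in the other direction would be of no interest. At end of treatment the sponsor can argue that. At follow-up the protocol's own literature review names the opposite result as a live possibility. The comparator is also an established active treatment (section 2.2.1), so a worse 6-month outcome under IPI would matter for practice.

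As planned, a deficit on HAM-A at week 34 leads formally only to a failure to show superiority. That is the same formal result as no difference at all. Without an interval for the arm difference, the report would give a signed standardised effect but no statement of how large a deficit, or benefit, is compatible with the data. Section 2.3's own non-directional aim, to show that the treatments differ, is not served by a one-directional test alone.

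**Working it through.** **Inputs.** Difference 2 points (reductions of 12 and 10), SD 10, 310 per group, one-sided 5%, power 80%: all from section 2.2.8. Section 2.2.10 counts the 620 as patients with post and follow-up data, so 310 per arm is also used at week 34. The documents give no follow-up effect or SD. I assume SD 10 there and a range of deficits.

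**1. The plan's own figure.** n per group = 2 × SD² × (z for alpha + z for power)² / difference² = 50 × (z for alpha + z for power)².
- One-sided 5%: 50 × (1.6449 + 0.8416)² = 309.1, rounded up to 310. This reproduces the plan.
- Two-sided 5%: 50 × (1.9600 + 0.8416)² = 392.4, rounded up to 393.
- One-sided at the printed 0.5: 50 × (0 + 0.8416)² = 35.4, rounded up to 36.

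So the sample size rests on one-sided 5%, and 0.5 is not the level behind it. Taken literally, 0.5 would favour IPI in half of all trials with no true difference.

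**2. Standard error of the arm difference.** 10 × √(2/310) = 0.803 points.

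**3. The planned test if IPI is worse.** With a true deficit of 2 points, the probability of rejection is 1 − Φ(1.645 + 2/0.803) = 1 − Φ(4.135) = 0.00002. Any such rejection would wrongly favour IPI. The probability of concluding that IPI is worse is zero by construction.

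**4. What a two-sided 95% interval adds.** Half-width = 1.960 × 0.803 = 1.57 points. The interval lies wholly on TAU's side with probability Φ(deficit/0.803 − 1.960):

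| True deficit of IPI (points) | Probability |
|---|---|
| 0 | 2.5% |
| 1 | 23.7% |
| 2 | 70.2% |
| 3 | 96.2% |

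**5. The alternative of a two-sided test at follow-up.** At 310 per arm, power for a 2-point benefit falls from 80.1% to 70.2%. The difference detectable with 80% power becomes (1.960 + 0.842) × 0.803 = 2.25 points.

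**6. Week-34 difference versus return of fear.** Suppose the planned reductions of 12 and 10 are reached at post and both arms stand at a reduction of 10 at week 34 (an illustration). The week-34 difference is 10 − 10 = 0, although IPI has lost 2 points since post and TAU none. Conversely, an arm that is worse at post and then stable is worse at week 34 with no return of symptoms. Persistence needs the arm difference in change from post to week 34. Table 1 schedules HAM-A at both times, so the planned mixed model can give it. Its precision depends on the correlation between the two visits, which the documents do not state, so no half-width is given here.

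**The case against.** The strongest reply is that the plan is not blind to harm. Cohen's d at follow-up carries a sign, the saturated mixed models estimate the follow-up contrast, and section 2.3 makes secondary and explorative tests two-sided. This stands, and it limits the point: what is missing is formal inference on HAM-A, not any sight of a deficit. A reader might infer that the trial could not answer its question about persistence at all. The documents do not support that. The two-sided secondary tests are a weaker safeguard than they look, because they do not cover HAM-A and the Summary confines two-sided tests to explorative analyses.

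Second, the statements on return of fear concern massed or condensed exposure in general, while IPI adds spaced trials afterwards, and section 1.1 cites mouse data in favour of that sequence. This also stands. A reader might infer that the protocol expects IPI to do worse in the long term; it does not. But the spaced trials are part of what is under test, and they do not give the test a second direction. Sections 2.1.1 and 2.2.2 describe spaced-exposure instruction around the boosters without naming an arm, whereas the Summary and section 2.2.1 say that TAU receives none. These passages must be reconciled.

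Third, a two-sided follow-up test would cost about 10 percentage points of power on part of the primary hypothesis. That is a fair reason not to insist on it.

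**Conclusion.** The point holds in a limited form. On the primary measure, the plan has no formal way to conclude that IPI is worse at 6 months, although its own rationale names that direction as possible. One-sided testing is not an arithmetic error: 310 per group reproduces under it. Nor do the documents compel a two-sided test at follow-up.

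The size rests on SD 10, 310 per arm at week 34, a 5% level and assumed deficits. Under these, an interval would reveal a 2-point deficit with probability of about 70%, and deficits of 1 and 3 points with about 24% and 96%. If 0.5 were the true level, the planned test would reject in IPI's favour with probability of about 0.006 at a 2-point deficit, and it still could not declare IPI worse.

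A reader might also take an interval favouring TAU at week 34 as evidence of greater return of fear. Step 6 of the working shows why it is not: it is a worse 6-month outcome and no more.

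**What to change.** In section 2.3:

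- Keep the planned one-sided tests, and state their level as the 5% of section 2.2.8, correcting or explaining the 0.5 printed in sections 0 and 2.3.
- Report the IPI–TAU difference in HAM-A, in points, with a two-sided 95% confidence interval at post and at week 34.
- State that an interval wholly in TAU's favour at week 34 is read as a worse 6-month outcome under IPI, not as return of fear.
- To address persistence, report from the planned mixed model the between-arm difference in change from post to week 34, with a two-sided 95% interval.
- State that superiority is decided by the one-sided test. An observed benefit between 1.32 points (1.645 × 0.803) and 1.57 points would pass that test while the 95% interval still included zero.

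The cost is a few lines of text and a little more reporting, with no extra patients or visits and no loss of power. The reading rule carries a 2.5% chance of wrongly calling IPI worse at week 34 when there is no difference. If the sponsor prefers a two-sided 5% test at follow-up, power there for a 2-point benefit falls from about 80% to about 70%. That is the sponsor's choice, and the stated end-of-treatment power is unaffected.

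### The alpha for the IPI versus TAU t-tests is printed as 0.5 in the Summary and section 2.3, against the one-sided 5% used to size the trial

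*Combined protocol and SAP*

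**What the plan says.** Three places in the combined protocol and SAP give a significance level for comparing IPI with TAU.

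- **Summary, Statistical analyses (primary efficacy):** "Superiority of IPI against TAU will be tested with t-tests for independent samples using an alpha level of 0.5". This sentence does not state a side.
- **Section 2.3:** for the HAM-A, "we use a one-tailed t-test with the following hypotheses", the alternative being a larger reduction under IPI. No level stands beside these hypotheses. For the major end points at post and follow-up, "t-tests for independent samples will be used one-sided with an alpha level of 0.5".
- **Section 2.2.8:** the calculation is introduced with "Using a power of 80%, a test significance level of" 5%. It assumes a 12-point HAM-A reduction under IPI, says "In the TAU group we expect a reduction by 10 points", takes an SD of 10, and concludes that for "a one-sided t-test to detect differences between the IPI and TAU group, a total of 310 patients are needed per group".

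For the other analyses, section 2.3 adds: "This will be also done for secondary and explorative analyses (in that case with two-sided tests". The Summary treats secondary endpoints like the primary one, "but with two-sided tests in case of explorative analyses". Neither place prints a separate level for these tests.

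**The concern.** A level of 0.5 is ten times the 5% that produced the sample size, and it stands in both places that set out how the primary comparison will be judged. No section gives 0.05 as the analysis threshold for IPI versus TAU. Anyone applying the analysis text as printed would therefore use a rule that provides no real control of false positives: a one-sided test at 0.5 rejects whenever the observed difference favours IPI at all. By cross-reference, the same 0.5 passes to the secondary and explorative tests.

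The sidedness of the secondary tests is a smaller matter. On its most natural reading, section 2.3 makes both secondary and explorative tests two-sided, whereas the Summary does so only for explorative ones.

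**Working it through.** **Inputs (section 2.2.8).** Expected reductions 12 and 10 points, so the difference is 12 − 10 = 2; SD 10, so the standardized difference is 2/10 = 0.2; power 80% (z = 0.8416); 310 per group.

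**Step 1: reproduce the plan's figure.** Per-group n = 2 × (z_alpha + 0.8416)² / 0.2². At one-sided 0.05, z_alpha = 1.6449, so n = 2 × (2.4865)² / 0.04 = 309.1, rounded up to 310. This matches.

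**Step 2: try the other readings.** The standard error with 310 per group is 10 × √(2/310) = 0.803 points. Power is approximately the normal probability below 2/0.803 − z_alpha = 2.490 − z_alpha.

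| Level and side | z_alpha | n per group (formula → rounded up) | Power with 310 per group |
|---|---|---|---|
| 0.05 one-sided | 1.645 | 309.1 → 310 | 80.1% |
| 0.05 two-sided | 1.960 | 392.4 → 393 | 70.2% |
| 0.5 one-sided | 0 | 35.4 → 36 | 99.4% |
| 0.5 two-sided | 0.674 | 114.9 → 115 | 96.5% |

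Of these four pairings, only one-sided 0.05 gives 310. The noncentral t distribution gives 310, 394, 36 and 107 per group (the last counts rejections in both tails), with powers within 0.1 percentage point of those shown. The conclusion is the same.

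**Step 3: what the printed rule would do.** There are 310 + 310 − 2 = 618 degrees of freedom.

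- One-sided 0.05: critical t = 1.647, so the smallest significant difference is 1.647 × 0.803 = 1.32 HAM-A points.
- One-sided 0.5: critical t = 0, so the smallest significant difference is 0 points.

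Probability of declaring IPI superior:

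| True difference (IPI minus TAU reduction) | At 0.5 | At 0.05 |
|---|---|---|
| 0 points | 50% | 5% |
| −0.5 points (IPI worse) | 26.7% | 1.2% |
| −1 point (IPI worse) | 10.7% | 0.2% |

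These rates are per test. The section 2.3 sentence covers both post and follow-up.

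**Step 4: secondary sidedness.** At 0.05 with 310 per group, the threshold for a secondary score is 1.32/10 = 0.132 SD one-sided. Two-sided it is 1.964 × 0.803 = 1.58 points on an SD of 10, or 0.158 SD.

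**The case against.** The strongest reply is that this is a transparent typing error with little practical consequence. Section 2.2.8 gives 5%; section 2.3 uses 95% confidence intervals for moderator effects; section 5.4 uses a corrected p < 0.05 for the genetics project. A plan to analyse 620 patients makes no sense for a test that needs 36 per group. Nobody is likely to run the test at 0.5, so the 50% and 26.7% figures describe a hypothetical. No calculation in the plan is wrong; the fault is an inconsistency between sections.

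Most of this stands. The intended value can be recovered, and the error rates above show what the printed rule means, not what is likely to happen. It does not make the text correct. The confidence intervals and the genetics threshold do not govern the IPI versus TAU tests, and a reader has to override two matching statements in the analysis text with a figure from the sample-size paragraph. The same value in two separate sentences also makes a PDF-reading fault unlikely.

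Two points of reading are also fair. The Summary's alpha sentence names no side, so the one-sided 0.5 comes explicitly from section 2.3 only. And the parenthesis there about two-sided tests could be read as covering explorative analyses alone, which would agree with the Summary. The sidedness point is therefore one of ambiguity and remains minor.

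**Conclusion.** The concern holds. The primary decision threshold is wrong as printed in the Summary and in section 2.3, and it contradicts the one-sided 5% on which 310 per group depends. It is almost certainly a misprint for 0.05. The practical risk is low, but the figure must be corrected because it is the only analysis level printed for the primary endpoint. Read literally, it moves the smallest significant difference from about 1.32 HAM-A points to zero and the per-test false-positive rate from 5% to 50%. These figures rest on the plan's own SD of 10, 310 analysed patients per group and a two-sample t-test with equal variances.

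**What to change.** 1. In section 2.3, change 0.5 to 0.05; the sentence already says one-sided.
2. In the Summary's primary efficacy statement, change 0.5 to 0.05 and add that the test is one-sided, to match section 2.2.8.
3. State 0.05 as the level for secondary and explorative tests as well, so that nothing inherits the misprint.
4. Make the Summary and section 2.3 agree on whether secondary tests are one- or two-sided. The choice is the sponsor's: section 2.3 most naturally reads as two-sided, while the Summary and its directional hypothesis for secondary outcomes are compatible with one-sided tests.

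The cost is two corrections to the alpha, a short statement of the level for the other tests, and one phrase on sidedness. Sample size, power, patients and procedures are unaffected.

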## 0. Summary

APPLICANT/ COORDINA- TING INVE- STIGATORS	[name]. [name] & [name]. [name] (Co-PI) Institute of Clinical Psychology and Psychotherapy & CELOS Technische Universität Dresden [name] [contact]; [contact] [contact]
TITLE	Optimizing Extinction Using Intensified Psychological Interventions (IPI) for Adult Anxiety Disorders (AD)
CONDITION	DSM-5: Panic Dis. (PD), Generalized Anxiety Dis. (GAD), Agoraphobia (AG), Social Anxiety Disorder (SAD), Specific Phobias (SP), Separation Anxiety Dis.(SepAD), and associated comorbid conditions
OBJECTIVE	To examine the efficacy of intensified psychological interventions (IPI) aiming to augment extinction learning during exposure. In IPI we increase the number of exposure trials and decrease the spacing between sessions providing more “extinction trials” over a shorter duration. To stabilize treatment effects we provide spaced exposure training during follow-up (booster) in different contexts. We also based exposure on a positive prediction error model. We hypothesize that IPI results in stronger, faster and more pervasive effects in subjective, behavioural, physiological, neural and epigenetic indices at post and follow-up via optimizing extinction learning. To test the hypothesis, we propose a multicentre randomized clinical trial (RCT). Patients will be randomly allocated to either IPI or standard research exposure treatment as usual (TAU) as the control condition. Primary hypotheses: (1) IPI will be superior to TAU at post and follow-up on primary and secondary outcome measures and will recover faster. Secondary hypotheses are: (2) IPI is associated with enhanced positive prediction error to increase extinction learning during and after exposure and (3) will result in more pronounced changes in behavioural proxy measures (between session reduction of fear, anxiety, avoidance) of extinction learning. We also explore the effect of type of diagnosis and comorbidity as potential moderators of outcome and extinction. We further expect that IPI will be associated with lower direct and indirect health care costs.

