symptomatic clinical cases. It remains unclear whether enhanced extinction is beneficial in all AD as well as comorbid patterns. (5) Patients with AD - at least in Germany - rarely receive appropriate anxiety treatment. In fact, studies have shown that exposure treatments are rarely applied at all, and if they are applied they seem to be provided without alignment with research standards or theory. This suggests indirectly that they might fail to stimulate appropriately presumed core mechanisms of action. Routine treatments in Germany are typically much longer (>50 weeks vs. RCT: 4-16), contain little to no exposure, are not manualized, and have considerably lower effect sizes. This might be at least partially due to the historically established practice, reinforced by insurance regulations favoring psychotherapy sessions of 50 min. once a week irrespective of method and diagnosis applied. This practice is unlikely to promote effectively essential mechanisms of fear inhibition. Clinical research has so far had little impact to change this situation.

The proposed trial will address these critical issues by conducting a multicenter randomised clinical trial (RCT) in typical patients of anxiety clinics to test whether efficacy adjustments in exposure-based treatment packages, targeting elements of enhanced extinction learning, lead to superior results. At the same time the RCT will provide the data to address - within projects P3, P4 and P5 - the key question of extinction as a core mediating process as well as questions regarding moderators (i.e. diagnostic pattern, comorbidity). A resolution of these questions is expected to have significant effects on patients with AD and the way exposure-based treatments are used in the psychotherapy sector.

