## **3. Add-on project Psychophysiology (P3): Behavioral and psychophysiological markers of extinction learning and outcome**

### **3.1 Background and aims**

The most effective treatment of anxiety disorders share exposure techniques as a core ingredient. Exposure treatment needs to be tailored in a way to promote extinction learning and prevent return of fear. The current research proposal aims to investigate the process of extinction learning across a large group of anxiety disorder (AD) patients prior to and after exposure therapy. We want to assess extinction learning at all levels of the emotional network, including verbal report (US-expectancy ratings), physiological arousal (sympathetic nervous system activity), and amygdala dependent modulation of defensive reflexes (fear potentiated startle). We expect that extinction learning is impaired in AD patients and will improve after exposure therapy. We hypothesize that extinction learning will improve to a greater degree after IPI than TAU. We expect that the response output measures are related to neural network activation (see P4). We expect extinction learning parameters being related to moderators of clinical outcome.

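### Section 2.3's moderator analyses estimate prognosis, not how the IPI-TAU difference varies, and section 3.5 ties P3's arm hypothesis to no test with arm and visit

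*Combined protocol and SAP*

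**What the plan says.** **Moderators.** The Summary states an exploratory aim: "We also explore the effect of type of diagnosis and comorbidity as potential moderators of outcome and extinction". Section 1.3 lists this among the open questions: "It remains unclear whether enhanced extinction is beneficial in all AD as well as comorbid patterns". Section 1.2, which is headed as being about moderators, puts a different question: whether depression and other comorbid patterns go with poorer outcomes of exposure treatment.

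Section 2.3 defines the analyses: "Moderator analyses (predictors of treatment effects within IPI and TAU patients) will address type, respectively group of disorders as well comorbidity". It then names the methods. For dimensional measures: "Pearson correlations between such comorbidity measures and outcome will be calculated". For categorical ones: "Associations with categorical predictors will be analyzed with linear regressions using dummy variables and quantified with mean differences in treatment outcome", with 95% confidence intervals. It also plans a general regression: "Individual outcome as a function of pretreatment characteristics will be modeled with multiple linear regression and associated analyses of variance". The Summary repeats the correlations and regressions. The only model in 2.3 that crosses group with another factor is the group-by-time mixed model. It serves to check the effect of dropout and contains no moderator.

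**P3.** Section 3.1 sets out to "investigate the process of extinction learning across a large group of anxiety disorder (AD) patients prior to and after exposure therapy". It then states: "We hypothesize that extinction learning will improve to a greater degree after IPI than TAU". Section 3.5 specifies repeated-measures analyses of variance with Phase and Cue, and with phase and context for the virtual-reality (VR) paradigm. It adds mixed models or correlations for differences between patients, with diagnosis, severity, comorbidity, chronicity and depression as examples. Treatment arm and therapy visit do not appear.

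**The concern.** A moderator of a treatment effect is a factor along which the difference between arms changes. A correlation or regression of outcome on a baseline factor estimates something else: whether patients with that factor do better or worse on average. If 2.3 is followed as written, a factor that only predicts outcome could be reported as a moderator with no estimate of how the IPI-TAU difference depends on it. A factor that does change the difference could go unnoticed.

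In P3 the hypothesis compares two changes, before to after therapy in IPI and in TAU. A model with neither arm nor visit cannot express that comparison. P3 has several outcome measures and test phases, so the comparison that decides the hypothesis could be chosen after the data are seen.

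**Working it through.** **Inputs.** Section 2.2.8 gives expected HAM-A reductions of 12 points (IPI) and 10 points (TAU), SD 10, one-sided 5%, power 80%, 310 per group and 620 analysed. Section 2.3 makes exploratory tests two-sided. It prints alpha as 0.5; I use the 5% of 2.2.8, which reproduces the sample size. Moderator prevalence and the share of each diagnosis are not given, so the values below are assumptions.

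**1. The plan's own figure.** n per group = 2 × SD² × (1.645 + 0.842)² / difference² = 2 × 100 × 6.185 / 4 = 309.3, so 310. It reproduces.

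**2. What the two kinds of analysis detect.** The SE of the overall arm difference, and of the average association with a 50:50 factor, is 10 × √(4/620) = 0.803. The SE of the arm-by-factor interaction is 0.803 × √(1/p + 1/(1−p)), which is 0.803 × 2 = 1.606 at p = 0.50. Simulation: 1,500 runs, N = 620, SD 10, p = 0.50, arm effect 2 points, two-sided 5%.

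| Truth | Outcome on predictor, significant | Arm-by-predictor, significant |
|---|---|---|
| Prognostic only, 3 points | 95% | 6% |
| Effect modification only, 4.5 points, no average association | 4% | 81% |

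The formulas agree: 3/0.803 = 3.7 SE for the prognostic factor, and 4.5/1.606 = 2.8 SE for the interaction.

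**3. A factor that acts in one arm only.** If the 4.5 points arise only in IPI, the average association is 4.5/2 = 2.25 points, and 2.25/0.803 = 2.8 SE. The regression would then usually be significant, but could not tell this factor from a prognostic one.

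**4. Separate analyses in each arm.** Suppose the true correlation is the same in both arms (310 each). Power per arm is Φ(atanh(r) × √307 − 1.96): 42%, 75.4% and 94.4% at assumed r = 0.10, 0.15 and 0.20. The chance that exactly one arm is significant, 2 × power × (1 − power), is about 49%, 37% and 11%. Comparing significance between arms therefore does not replace the interaction.

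**5. What an interaction test would deliver.** Binary moderator, 620 analysed, two-sided 5%:
- 50:50 split: SE 1.606; power for 2 points 24%; 95% CI ±1.96 × 1.606 = ±3.1.
- 20:80 split: SE 0.803 × 2.5 = 2.008; power 17%; 95% CI ±1.96 × 2.008 = ±3.9.
- 80% power needs about 4.5 points (50:50) or 5.6 points (20:80).

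**6. Arm difference within one diagnosis.** CI = ±1.96 × 10 × √(2/n), n per arm:
- share one sixth: n = 51.7, ±3.9 points
- share 10%: n = 31, ±5.0 points
- share 5%: n = 15.5, ±7.0 points

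**7. P3.** No arithmetic applies, because the documents give no effect size or SD for its measures. The hypothesis in 3.1 needs arm (IPI, TAU), visit (before, after therapy) and the CS+/CS− contrast during extinction. Section 3.5 supplies only the last of these, through Phase and Cue.

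**The case against.** Four points deserve weight.

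- **Prognosis may be what is meant.** The Summary says only that moderators of outcome are explored, and section 1.2 asks about poorer outcomes. The named correlations and regressions answer that question and should stay. But 2.3 itself speaks of predictors of treatment effects, and 1.3 asks where enhanced extinction is beneficial. The second question is within the aim and has no named analysis.
- **An interaction is not excluded.** A reader might infer that the plan rules it out. It does not. If the regressions are run in each arm, the difference between the two arm-specific estimates is the interaction. The plan does not say that this difference will be estimated, and Pearson correlations do not give it in HAM-A points.
- **A reader might infer that P3's arm hypothesis has no test at all.** That goes too far. Section 2.3 extends two-sided between-group t-tests to secondary and exploratory analyses, and such a test on change scores could serve. Section 3.5, which governs the P3 measures, does not invoke it. Its list of patient characteristics is open, but randomised arm is not a patient characteristic, and the list cannot supply the missing visit factor.
- **Low power and low rank.** Moderators are exploratory and P3 is an add-on project. This stands: it limits what the fix can deliver and how urgent it is. It does not make a prognostic coefficient an answer to a question about the arm difference.

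**Conclusion.** The concern holds in this form. The analyses named in 2.3 answer the prognostic question of 1.2, but do not estimate how the IPI-TAU difference varies with diagnosis or comorbidity. Read as regressions over both arms, they would usually flag a purely prognostic factor (95% of runs at 3 points) and usually miss an effect modifier with no average association (4% at 4.5 points). In 3.5 the hypothesis of greater improvement after IPI is not tied to a test with arm and visit.

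These figures rest on SD 10, 620 analysed, equal arms and an assumed 50:50 factor. The precision for any one diagnosis depends on shares that the documents do not give.

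Two further inferences are not supported. A reader might want a power figure for P3, but beyond the missing effect size and SD, the usable sample differs by measure. Table 2 shows that startle and heart rate are not recorded in the scanner, and 3.1 places VR at four sites. The roughly 300 patients in 4.2 are the imaging subset and not the P3 sample. A reader might also extend the point to faster recovery. That is a separate matter: Table 1, as available, does not show which generic scales are collected at week 8, and 2.1.1 has the IPI exposure module ending four weeks before TAU's.

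The primary HAM-A test is untouched. The change should be made, but the trial does not depend on it.

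**What to change.** **Section 2.3.** Keep the correlations and regressions, and label them prognostic. Add, in all randomised patients, a model with arm, moderator and arm-by-moderator for diagnosis type (or group of disorders) and for comorbidity.
- For binary or continuous moderators, report the interaction estimate with its 95% CI.
- For diagnosis, report a joint interaction test and the arm difference with 95% CI in each group.
- List the moderators in advance, label the analyses exploratory and report how many were tested.
- Claim no equal benefit from a non-significant result.

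**Section 3.5.** Add arm and pre/post-therapy visit, and test arm × visit × Cue during extinction.
- For startle and heart rate, restrict this to patients who complete extinction in the laboratory.
- For skin conductance and expectancy ratings, use all patients and account for laboratory or scanner setting.
- For VR, add arm × visit × Context at the four VR sites only if the paradigm is repeated after therapy. Section 3.3 places it on day 1 only and does not state a repeat.

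**Cost.** Wording only, with no new patients. The price is low power, so the moderator product is estimates with wide intervals and not a verdict. Several tests also add false positives: five independent ones at 5% give 1 − 0.95⁵ = 22.6% for at least one, hence the advance list and the reported count.
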